4.1.1.1 Composition of Dose Escalation Committee

Proceeding to the next higher dose requires an agreement of the DEC, which is comprised of Sponsor representatives. The DEC Charter will provide detailed additional information.

4.1.1.2 Decision Process for Dose Escalation and MAD Initiation

The DEC will decide dose escalation and the initiation and selection of doses for MAD cohorts based on emerging safety and tolerability data from SAD. After all subjects in a cohort have been dosed and completed study procedures through Day 15, the overall safety and tolerability of the dose will be determined after evaluation of the blinded safety data [treatment emergent adverse events (TEAEs), adverse events (AEs) of special interest, otology examinations (imaging pictures of tympanic membrane, bone conduction hearing at 1, 2, 4 kHz by PTA, TVAS, Modified Brighton Grading Scale, and vital signs] for the current cohort. Cumulative AE data from the preceding cohort(s) will also be included in the assessment for dose escalation. Details will be defined in the DEC Charter.

4.1.1.3 Dose Escalation Stopping Rules

Depending on the nature, frequency and severity of the safety profile observed in the study, the DEC will decide whether to:

- Proceed with dose escalation and determine the next higher dose or,
- Stop dose escalation (i.e., no further dosing with IP).

Dose escalation will be stopped if 1 (or more) of the following apply:

- If 1 or more subjects in 1 cohort develop cholesteatoma or suspicion of ear neoplasm which is considered to be related to the ASP0598.
- If 2 or more subjects in 1 cohort develop Ototoxicity (clinically significant report of vestibular symptoms, tinnitus, or acute hearing loss) which are considered to be related to the IP.

- If 2 or more subjects in 1 cohort develop persistent otitis media or otitis externa unresponsive to oral and topical antibiotics which is described in concomitant treatment requirements section of the synopsis which are considered to be related to the IP.
- If 1 or more subjects in 1 cohort experience AEs of severe intensity or 2 or more subjects in 1 cohort experience AEs of the same character of moderate intensity, which are considered to be related to the IP, and of clinical concern.

In the event that it is deemed relevant to unblind a subject for the purposes of a dose escalation decision, the DEC chair or designee can request the treatment assigned to one or more subjects from the study statistician. The DEC charter will include information on unblinding of study team members and other details.

4.1.1.4 Definition of the Maximum Tolerated Dose

If the DEC decides to stop dose escalation based on available safety data, the current dose level will be considered as the minimum intolerable dose (MID). The dose just below the MID will be regarded as the maximum tolerated dose (MTD). If the dose escalation is stopped due to reaching exposure limit without dosing limiting safety findings, MTD cannot be determined.

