6.3.1 Blinding Method

In order to maintain the blind, the ASP0598 Otic Solution and placebo will be received in the same volume and route from the pharmacist or designee. The pharmacist or designee will receive the unblinded treatment assignment from IRT in order to prepare the correct concentration of ASP0598 Otic Solution or placebo. The subject and investigator will be blinded to the treatment assignment.

Dose Escalation

Only one cohort will be enrolled at a time. The randomization number will be assigned based on information obtained from the IRT system.

Dose Expansion

Subjects will be randomized through the IRT system in a 1:1:1 ratio, if 3 treatment groups are selected or 1:1 ratio, if 2 treatment groups are selected based on the interim analysis.

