10 OPERATIONAL CONSIDERATIONS

10.1 Data Collection

The investigator or site designee will enter data collected using an electronic data capture system. In the interest of collecting data in the most efficient manner, the investigator or designee should record data (including clinical laboratory values, if applicable) in the eCRF within 5 days after the subject's visit. For SAD and MAD, the investigator or site designee must enter data collected into the RAVE data management system within 24 hours after the completion of the Screening, Day 1, Day 8 and Day 15 visits.

The investigator or site designee is responsible to ensure that all data in the eCRFs and queries are accurate and complete and that all entries are verifiable with the source. These documents should be appropriately maintained by the study site.

The monitor should verify the data in the eCRFs with the source and confirm that there are no inconsistencies among them.

Clinical laboratory tests are performed at the local laboratory. Clinical laboratory results will be documented in the subject's source records. All PK samples and additional samples collected for future analysis will be shipped to the central laboratory for storage and shipping to the laboratory responsible for analyzing the samples. PK data will be transferred electronically to the sponsor or designee at predefined intervals during the study.

All procedures conducted under the protocol must be documented.

The investigator or designee is responsible for eCRF and source data completion and will ensure that all data and queries are accurate, complete and are verifiable with the source. The source should be appropriately maintained by the study site.

Electronic data sources and any supporting documents should be available for review/retrieval by the sponsor/designee at any time.

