10.4 STUDY ORGANIZATION

10.4.1 Dose Escalation Committee

For SAD and MAD, the Dose Escalation Committee (DEC) is responsible for dose escalation decisions. The DEC will consist of Astellas team members and an advisor. For detailed information on the dose escalation decision process, refer to Section [4.1.1](#) Decision Process for Dose Escalation, Dose Escalation Stopping Rules and Definition of the Maximum Tolerated Dose. A separate DEC Charter will be maintained detailing the membership, roles, and responsibilities of the DEC.

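### Protocol 4.1.1.4 ties the MID to the dose level that is current at the stop, so a late trigger in the preceding cohort makes the triggering dose the MTD

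*Protocol*

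**What the plan says.** Protocol 4.1.1.4 and the matching synopsis paragraph fix two labels when the DEC stops on safety data: "the current dose level will be considered as the minimum intolerable dose (MID" and "The dose just below the MID will be regarded as the maximum tolerated dose (MTD". A further sentence says that no MTD can be determined if escalation ends at the exposure limit without limiting safety findings.

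Four other provisions decide which level is current when a stop occurs:

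- **Timing of review (4.1.1.2).** The DEC judges a dose "After all subjects in a cohort have been dosed and completed study procedures through Day 15".
- **Data reviewed (4.1.1.2).** The section separates the current cohort from earlier ones and adds: "Cumulative AE data from the preceding cohort(s) will also be included in the assessment for dose escalation".
- **Stopping rules (4.1.1.3).** Events are counted within any single cohort, for example "If 1 or more subjects in 1 cohort develop cholesteatoma or suspicion of ear neoplasm" judged related to ASP0598. The rules are not limited to the cohort under review.
- **Enrolment (6.3.1).** "Only one cohort will be enrolled at a time", so there is one current level.

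Adverse events are collected through Day 57 in SAD and Day 85 in MAD (Schedule of Assessments, footnote c of each table).

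**The concern.** The MID should be the lowest level found intolerable. The text instead takes the level in use when the DEC acts. The two are the same if the current cohort causes the stop. They differ if an earlier cohort meets a rule after its own Day 15 review, once the next level has opened. The higher level then becomes the MID on the strength of events it did not produce, and the level that met the rule becomes the MTD.

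Safety and tolerability is the primary objective (3.1), this is the first clinical study of the product (2.2), and the MTD is the only tolerability limit the protocol defines. Calling a dose maximum tolerated when it met a stopping rule would mislead anyone who later relies on that label.

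**Working it through.** The plan gives no figure for this rule, so there is nothing to reproduce. The check covers timing and then every case on the planned dose ladder.

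**1. Can a trigger come after the cohort's own review?**

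- SAD follow-up after dosing: 57 − 1 = 56 days. After Day 15: 57 − 15 = 42 days. 42/56 = 75%.
- MAD: 85 − 1 = 84 days. After Day 15: 85 − 15 = 70 days. 70/84 = 83%. The third dose (Day 29) also falls after Day 15, and the second falls on Day 15 itself.

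These are shares of observation days, not of risk. They show only that most follow-up comes after the review.

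**2. Is the earlier cohort still informative at the next review?** The next cohort needs at least 14 days from its own Day 1 to Day 15. If it starts on the day its predecessor is cleared, the predecessor's last subject is at Day 15 + 14 = Day 29 or later at the next review, ignoring visit windows. At least about 14 further days of that cohort's data then count as data from a preceding cohort.

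**3. What labels result?** The SAD ladder is 0.2, 1.0, 5.0 and 15 µg/mL (4.1, Table 6). The written rule uses the current level. The comparison rule uses the level that met a stopping criterion.

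| Current level | Level that met a rule | Written MID / MTD | MID / MTD by triggering level |
|---|---|---|---|
| 0.2 | 0.2 | 0.2 / none | 0.2 / none |
| 1.0 | 1.0 | 1.0 / 0.2 | 1.0 / 0.2 |
| 5.0 | 5.0 | 5.0 / 1.0 | 5.0 / 1.0 |
| 15 | 15 | 15 / 5.0 | 15 / 5.0 |
| 1.0 | 0.2 | 1.0 / 0.2 | 0.2 / none |
| 5.0 | 1.0 | 5.0 / 1.0 | 1.0 / 0.2 |
| 15 | 5.0 | 15 / 5.0 | 5.0 / 1.0 |
| 5.0 | 0.2 | 5.0 / 1.0 | 0.2 / none |
| 15 | 0.2 | 15 / 5.0 | 0.2 / none |
| 15 | 1.0 | 15 / 5.0 | 1.0 / 0.2 |

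- Trigger in the current cohort (4 cases): the two rules agree.
- Trigger one cohort back (3 cases): the written MTD equals the triggering dose.
- Trigger two or more cohorts back (3 cases): the written MTD is above the triggering dose.

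The volume is constant at 0.15 mL, so concentration ratios are dose ratios. In the two one-step cases where both rules give an MTD, the written value is 1.0/0.2 = 5 and 5.0/1.0 = 5 times the right one.

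**4. MAD.** If the definition applies there, and cohort 5 (5.0 µg/mL, Q2W×3) met a rule after Day 15 with a stop during cohort 6 (15 µg/mL), the written MTD would be 5.0. Judged within the regimen, the MID is 5.0 and there is no MTD unless a lower Q2W×3 level had been studied. None is planned, although 4.3 allows a lower MAD start.

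**The case against.** **The term is not defined, and a charter governs.** The protocol does not define the current dose level and leaves details to the DEC Charter, which is not among the documents. The charter may settle the matter. But 4.1.1.2 uses current in contrast to preceding, which favours the literal reading, and no protocol text ties the MID to the triggering cohort.

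**At the top level no escalation review follows.** After 15 µg/mL there is no higher level in the regimen, and so no later escalation decision that would bring in earlier cohorts' events. This stands: the 15 µg/mL cases need the DEC to stop during that cohort. The 1.0-with-5.0 case does not. However, the SAP 7.1 change list (6 July 2022) describes the Day 3 assessments of cohorts 1 to 3 as completed, so the lower SAD cases may already be behind the trial.

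**MAD coverage is mixed.** Protocol 4.1 speaks of escalating or stopping during SAD, and 4.1.1.2 bases MAD doses on SAD data. Against that, 10.4.1 says: "For SAD and MAD, the Dose Escalation Committee (DEC) is responsible for dose escalation decisions". Section 10.1 also requires entry of both SAD and MAD data "within 24 hours after the completion of the Screening, Day 1, Day 8 and Day 15 visits", which fits a Day 15 review in both parts. The MAD case rests mainly on 10.4.1.

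**A purely mechanical definition would create new faults.** The DEC may stop on the overall safety profile without a listed criterion being met, and it reviews blinded data from cohorts that include placebo subjects. A MID defined only by listed criteria would leave a discretionary stop without a label, or let a placebo subject's event set it. Both points stand, and the fix allows for them.

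**Stronger readings the documents do not support.** A reader might infer that subjects would be given a dose that is too high. No text uses the MTD to cap a dose: 4.3 limits MAD by the maximum feasible dose or the NOAEL, 4.2 leaves the opening of expansion to the Data Monitoring Committee, and a stop means no further dosing. The SAP has no MTD analysis, and events are tabulated by treatment group, so the triggering event stays visible. A reader might also want a probability for a late trigger. The documents give no event rates, so none can be stated.

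**Conclusion.** The point holds as a fault in a stated definition. Read literally, 4.1.1.4 and the synopsis give the wrong MTD whenever an earlier cohort meets a rule late and the DEC stops while a higher level is current. In all three one-step cases on the SAD ladder, the triggering dose becomes the MTD.

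The conclusion assumes that current means the level being given or reviewed, that the DEC Charter does not say otherwise, and that the next level has already opened when the DEC acts. If it has not opened, the triggering level is still current and the written rule is right. Application to MAD is likely but not certain.

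The consequence is a wrong tolerability label, not a wrong dose for any subject. It is worth correcting because the label describes the primary objective and the correction is cheap.

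**What to change.** Replace the first two sentences of the definition in 4.1.1.4 and in the synopsis with wording such as:

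> When safety data lead the DEC to stop escalation, the MID is the lowest dose level, within the same regimen (single or Q2W×3), at which a stopping criterion was met in any cohort. If no listed criterion was met, the MID is the level whose safety data led the DEC to stop. The treatment assignment of each triggering subject is confirmed by unblinding before the label is assigned; events in placebo subjects do not set the MID. The MTD is the next lower level studied in that regimen; if there is none, no MTD is determined. Both labels are confirmed on complete follow-up of all escalation cohorts.

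Keep the exposure-limit sentence, the stopping rules and the dose limits in 4.3 as they are, and put the same wording in the DEC Charter. The cost is these few sentences plus limited unblinding, which 4.1.1.3 already lets the DEC chair or designee request from the study statistician. No new data, visits or subjects are needed. If the current cohort alone causes the stop, through events in ASP0598 subjects, the labels stay as they are now.

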4.2 Decision Process for Dose Expansion

A Data Monitoring Committee (DMC) will be implemented and is responsible for the interim evaluation of safety and efficacy data and decision to open single and/or multiple dose expansion. The DMC membership will be described in a separate DMC Charter.

Two interim analyses will be conducted. The analyses will be performed after completion of last cohorts from of SAD and MAD, respectively.

The analysis will be conducted by the Astellas study statistician, with results reviewed by the DMC as per IAP. Details of the interim analysis procedure and the criteria to open single and/or multiple dose expansion will be described in the DMC charter.

4.3 Dose Rationale

SAD

The starting dose for SAD is 0.2 µg/mL administered in a single 0.15 mL dose volume. This starting concentration is equivalent to the minimum efficacious concentration in a nonclinical pharmacology study in a mouse CTMP model (minimum efficacious dose = 0.2 µg/mL, 5-µL single-dose volume). The dose volume has been scaled for clinical application based on tympanic membrane surface area between mice (3 mm^2) and humans ($68.3 - 90 \text{ mm}^2$).

The nonclinical pharmacology study showed concentration-dependent efficacy of ASP0598 [Section 2.1.1]. In addition, given the nature of ASP0598 Otic Solution as a topical agent with local exposure and toxicity, the concentration (µg/mL) of ASP0598 Otic Solution was used as the basis for selecting the doses for the first-in-human study.

GLP studies were conducted to evaluate the toxicity after single-dose administration of ASP0598 Otic Solution in 2 different species: mice and cynomolgus monkeys [Section 2.1.1]. The no adverse effect levels (NOAEL) were determined in the GLP toxicity studies as follows:

- NOAEL after a single administration into external auditory canal:
150 µg/mL administered in a 10-µL volume in mice.
150 µg/mL administered in a 100-µL volume in cynomolgus monkeys.
In both species, the NOAEL was the highest concentration tested in the study.
- NOAEL after a single transtympanic dose administration:
150 µg/mL administered in a 2-µL volume in mice.
150 µg/mL administered in a 100-µL volume in cynomolgus monkeys.
In both species, the NOAEL was the highest concentration tested in the study.

The first-in-human starting concentration of 0.2 µg/mL has a 750-fold safety margin over the NOAEL concentration from the GLP toxicity studies.

The first-in-human maximum concentration is tentatively set at a concentration 15 µg/mL in a 0.15 mL volume dose, which is the maximum feasible concentration in the clinic. This maximum concentration has a 10-fold safety margin over the NOAEL concentration from the GLP toxicity studies. Dose adjustments will be based on altering the concentration of ASP0598 in the solution to 1.0, 5.0, and 15 µg/mL while the administration volume will be held constant at 0.15 mL. More than a 3-fold dose-increment, especially at lower concentration levels, is considered acceptable, considering the large safety margin as well as the non-steep concentration-response relationship observed in the CTMP mouse model.

MAD

The initiation and selection of dose concentrations for MAD will be based on emerging safety and tolerability data, and at least 3 dose cohorts of SAD should be available for the decision to initiate MAD. The starting dose of MAD will be 5.0 µg/mL or lower, and another dose concentration up to the maximum feasible dose (15 µg/mL) or the NOAEL, whichever is lower, will be selected. The toxicology profile associated with repeat doses of ASP0598 given 3 times at 2-week intervals has been tested in CBA/CaJ mice and cynomolgus monkeys and did not produce any significant toxicological findings. A bi-weekly dose schedule is selected that is considered convenient for patients and otolaryngology clinics, and it is predicted to resemble single treatments with minimal chance of drug accumulation. Therefore, Q2W × 3 is selected for the dose frequency of the multiple dose.

4.4 End of Study Definition

End of the study is defined as the last visit or scheduled procedure shown in schedule of assessments for the last subject in the study.

5 STUDY POPULATION

All screening assessments must be completed and reviewed to confirm the potential subject meets all eligibility criteria. Prospective approval of protocol deviations (PDs) to eligibility criteria (also known as protocol waivers or exemptions) is not permitted.

5.1 Inclusion Criteria

A subject is eligible for the study if all the following apply:

1. Institutional Review Board (IRB)/Independent Ethics Committee (IEC) approved written Informed Consent and privacy language as per national regulation (e.g., Health Insurance Portability and Accountability Authorization for US sites) must be obtained from the subject or legally authorized representative prior to any study-related procedures (including withdrawal of prohibited medication, if applicable).
2. Subject must be 18 to 75 years of age at the time of informed consent.
3. Subject has chronic tympanic membrane perforation (CTMP) documented as persisting longer than 3 months.
4. A female subject is eligible to participate if she is not pregnant see Appendix [12.3: Contraception Requirements](#) and at least one of the following conditions applies:
 - a. Not a woman of childbearing potential (WOCBP) as defined in Appendix [12.3: Contraception Requirements](#) OR
 - b. WOCBP who agrees to follow the contraceptive guidance as defined in Appendix [12.3: Contraception Requirements](#) starting at screening and for at least 28 days after investigational product (IP) application.
5. Female subject must agree not to breastfeed starting at drug application on Day 1 and for at least 28 days after IP application.
6. Female subject must not donate ova starting on Day 1 and for at least 28 days after IP application.
7. A male subject with female partner(s) of child-bearing potential must agree to use contraception starting on Day 1 and for at least 28 days after IP application as detailed in Appendix [12.3](#).
8. A male subject must not donate sperm starting on Day 1 and for at least 28 days after IP application.
9. Male subject with a pregnant or breastfeeding partner(s) must agree to remain abstinent or use a condom from Day 1 and for at least 28 days after IP application.
10. Subject must be willing and able to comply with the study requirements including refraining from using prohibited concomitant medications.
11. Subject agrees not to participate in another interventional study during the study period.

12. Subject has the ability to understand and the willingness to sign a written informed consent document.

Waivers to the inclusion criteria will NOT be allowed.

5.2 Exclusion Criteria

A subject will be excluded from participation if any of the following apply:

1. Subject has one of following conditions, that is confirmed by the investigator, that may affect the ipsilateral side of the ear with CTMP:
 - a. Perforation involving 3 or more quadrants.
 - b. Pin hole perforation (only for the expansion cohort).
 - c. Presence of tympanosclerosis adjacent to the perforation.
 - d. Perforation involves malleus erosion.
 - e. Absent malleus.
 - f. Marginal perforation (i.e., involving the annulus or exposing the handle of malleus).
 - g. TMP caused by electric/slag/blast/burn injury.
 - h. Post radiated TMP.
 - i. History of tympanic membrane repair by any type of live tissue.
 - j. Active otorrhea or active treatment for otorrhea within the last 3 months prior to Screening.
 - k. Bellucci otorrhea grade 3 or above.
 - l. Active external ear canal inflammation (otitis externa, dermatitis) or within the last 3 months prior to Screening.
 - m. Active diagnosis of Eustachian Tube dysfunction or diagnosis within 6 months prior to Screening.
 - n. Craniofacial abnormalities, history of head and neck surgery within the last 3 months prior to Screening, history of radiation to head and neck.
 - o. Recent (within 2 weeks) diagnosis of upper respiratory tract infection.
 - p. Presence or history of cholesteatoma.
 - q. Presence of pars-flaccida or pars tensa retraction or adhesion.
 - r. Presence or history of tumors of the middle or external ear.
 - s. Contraindications to tympanic membrane closure.
 - t. An audiometric finding indicates a characteristic of Carhart's notch which is an increase in bone conduction threshold with a peak at 2,000 Hz.
 - u. Only hearing ear or better hearing ear and the contralateral ear ≥ 40 dB by average four-frequency (500, 1000, 2000 and 4000 Hz).
 - v. Whole circumference of the tympanic membrane perforation is not visible by endoscope.
 - w. Presence/history of eosinophilic otitis media in either ear.
2. Subject has a presence of adhesive otitis media in the contralateral ear.
3. Subject has a presence of any wound healing systemic condition.

4. Subject has Obstructive Sleep Apnea where the subject is required to use Continuous Positive Airway Pressure (CPAP) during the study period.
5. Subject is exposed in their daily life to high volume of water into the ear canal (e.g., swimmer or surfer).
6. Subject has health conditions that would prevent him/her from fulfilling the study requirements as judged by the clinical investigator on the basis of medical history and laboratory test (Serum Chemistries, CBC with Differential, Urinalysis) results at the screening visit.
7. Subject is receiving any other investigational agents during study participation.
8. Subject has any form of substance abuse, or psychiatric illness/social situations that would limit compliance with study requirements, or a condition that in the opinion of the investigator could invalidate communication with the investigator.
9. Subject has a known or suspected hypersensitivity to ASP0598, or any components of the formulation used.
10. Subject has had previous exposure with ASP0598.
11. Subject is unlikely to comply with the visits scheduled in the protocol, in the opinion of the Investigator.

Waivers to the exclusion criteria will NOT be allowed.

